5.7 Other Analyses

measures in Section 5.4.1.2.

5.7.1 Health Outcomes/Quality of Life

The health outcome and quality of life measures including CC

and Inflammatory Bowel Disease Questionnaire

(IBDQ) will be analyzed using methods described for continuous data as described for efficacy

5.7.2 Efficacy Subgroup Analyses

Subgroup analyses may be conducted for the co-primary endpoints in the PAS sub-population (Section 4). The following groups will be considered for subgroup analyses:

- Not-Biologic-Failed Population: Participants who have not failed any biologic medication regardless of prior biologic exposure.
- Biologic-Failed Population: Participants who have failed at least one biologic medication.

Some additional subgroup analyses may be performed to meet regulatory requirements in specific countries. The analysis of additional subgroups will not require an amendment to the SAP.

5.7.3 Reinduction Analysis

Patients from Study AMAM who did not achieve endoscopic response at Week 52 in Study AMAM were reinduced using mirikizumab 900 mg IV Q4W (3 doses). We will further investigate outcomes in patients who

- were randomized to mirikizumab in the AMAM Primary Analysis Set
- showed some initial response on mirikizumab
- lost the response or did not achieve further improvement at AMAM Week 52, and

• were re-induced in Study AMAX.

Several analyses will be performed, including

- proportion of patients achieving clinical response by patient-reported outcomes (PRO) at Week 12 in Study AMAX among:
 - o patients who achieved clinical response by PRO at Week 12 in Study CCl and
 - o who did not achieve clinical response by PRO at Week 52 in Study CCI.
- proportion of patients achieving clinical response by PRO at Week 12 in Study AMAX among:
 - o patients who achieved clinical response by PRO any time between Week 2 and Week 24 in Study CCI, and
 - o who did not achieve clinical response by PRO at Week 52 in Study CCl...
- Proportion of patients achieving clinical remission by PRO at Week 12 in Study AMAX among:
 - o patients who achieved clinical response by PRO at Week 12 in Study CCI, and
 - o who did not achieve clinical remission by PRO at Week 52 in Study CCI.
- Proportion of patients achieving clinical remission by PRO at Week 12 in Study AMAX among:
 - o patients who achieved clinical remission by PRO any time between Week 2 and Week 24 in Study CCI , and
 - o who did not achieve clinical remission by PRO at Week 52 in Study CCl...

Safety analysis may be performed for the corresponding subpopulations. The efficacy and safety analysis of additional subpopulation will not require an amendment to the SAP.

5.8 Interim Analyses

5.8.1 Data Monitoring Committee (DMC)

A DMC consisting of members external to Lilly is established for interim safety monitoring across Studies AMAM, and AMAX in participants with CD. This committee consists of 4 voting members, including a designated chairperson, 2 additional physicians with gastroenterology and/or clinical trial expertise, and a statistician. No member of the DMC may have contact with study sites. A Statistical Analysis Center (SAC) is external to the mirikizumab team that may be Lilly employees or from third-party organization designated by Lilly. No member of the SAC will have contact with study sites. Study AMAX is an open label study and safety data will be reviewed by the DMC. The DMC will advise Lilly regarding continuing participant safety; however, the DMC may request key efficacy data to put safety observations into context and to assess a reasonable benefit/risk profile for ongoing participants in the studies.

Study AMAX will not be stopped for positive efficacy. Study sites will receive information about interim assessment ONLY if they need to know for the safety of their participants. Details of the planned safety data analyses, the roles and responsibilities, and the data review process are included in the DMC Charter. Unblinding details are specified in a separated unblinding plan.

5.8.2 Analysis of the Primary Endpoint

One interim analysis is planned to be conducted CCl
Since Study AMAX is open-label, this analysis will be based on unblinded data.

5.8.3 Ad-hoc Interim Analysis

Additional ad-hoc interim analyses may be performed as deemed appropriate and/or to fulfill regulatory needs or for disclosure purposes. The final database lock will occur after the last participant has completed Study AMAX. A tiered database lock approach may be performed as deemed appropriate for interim analyses and the final database lock to allow additional data such as histology data to be transferred at a later date after the initial transfer. For early interim analysis where not all participants could have completed the time point of interest, participants who enrolled in AMAX after a specified date will be excluded from the analysis to ensure that all patients in the analysis could have completed the time point of interest. For the ad-hoc interim analysis in September 2024, the safety period will be 1 year of treatment.

- **6 Supporting Documentation**
- 6.1 Appendix 1: Description and Derivation of Efficacy and Health Outcome Endpoints

Measure	Description	Variable	Derivation / Comment	Definition of missing
SES-CD	The SES-CD is an endoscopic scoring system for CD based on 4 endoscopic variables (presence and size of ulcers, proportion of surface covered by ulcers, proportion of surface affected by disease, and presence and severity of stenosis), which are assessed in 5 ileocolonic bowel segments (ileum; right, transverse, and left colon; and rectum). Each of the 4 endoscopic variables is scored from 0 to 3: presence and size of ulcers (none = score 0; diameter 0.1 cm to 0.5 cm = score 1; 0.5 cm to 2 cm = score 2; >2 cm = score 3); extent of ulcerated surface (none = 0; <10% = 1; 10% to 30% = 2; >30% = 3); extent of affected surface (none = 0; <50% = 1; 50% to 75% = 2; >75% = 3); and presence and type of narrowing (none = 0; single, can be passed = 1; multiple, can be passed = 2; cannot be passed = 3). The endoscopic scores for each bowel segment are called subscores.	SES-CD total score	The sum of all endoscopic scores across all bowel segments. Total scores range from 0 to 56, with higher scores indicating more severe disease. SES-CD total score is calculated as average of total scores from all readers. AMAG 3-year endoscopy: 1. Endoscopies performed up to 4 weeks prior to the intended AMAG 3y timepoint (3 years after randomization in AMAG) or up to <4 years after randomization in AMAG 2. If not available, ETV/unscheduled endoscopies performed up to 4 weeks prior to intended AMAG 3y timepoint or up to <4 years after randomization in AMAG Week 52 endoscopy (AMAM-originating patients only) 1. Endoscopies performed up to 14 days after actual visit, with no additional dosing allowed prior to endoscopy (other than potentially the V9 dosing) 2. If not available, unscheduled/ETV endoscopies performed up to 14 days before or after actual V9 office visit, with no additional dosing allowed prior to endoscopy (other than potentially the V9 dosing) Week 156 endoscopy (AMAG/AMAM-originating patients) 1. Endoscopies performed up to 14 days after actual V19 office visit	Missing if endoscopy was not done at time point or if 2 or more central readers deemed the endoscopy video unreadable

Measure	Description	Variable	Derivation / Comment	Definition of missing
			2. If not available, unscheduled/ETV endoscopies performed up to 14 days before or after actual V19 office visit	
		Change from baseline in SES-CD total score	Change from baseline in SES-CD total score = SES-CD total score – baseline SES-CD total score	Missing if endoscopy was not done at baseline or time point or if 2 or more central readers deemed the endoscopy video unreadable
		Endoscopic Response	Endoscopic response is defined as ≥50% improvement from baseline in SES-CD total score. If [100* (SES-CD total score – baseline SES-CD total score) / baseline SES-CD total score] ≤ -50, then endoscopic response is achieved.	Missing if endoscopy was not done at baseline or time point or if 2 or more central readers deemed the endoscopy video unreadable
		Alternate endoscopic remission SES-CD ≤4	Endoscopic remission SES-CD ≤ 4 is defined as SES-CD Total Score ≤4 and at least a 2-point reduction from baseline and no subscore >1 for any variable in any segment. If SES-CD total score ≤ 4, SES-CD total score – baseline SES-CD total score ≤ -2, and each SES-CD subscore ≤ 1, then endoscopic remission SES-CD ≤ 4 is achieved.	Same as for endoscopic response

Measure	Description	Variable	Derivation / Comment	Definition of missing
		Endoscopic remission SES-CD ≤4	Endoscopic remission SES-CD \leq 4 is defined as SES-CD Total Score \leq 4 and at least a 2-point reduction from baseline and no subscore $>$ 1. If SES-CD total score \leq 4, SES-CD total score $=$ baseline SES-CD total score \leq -2, and each SES-CD subscore \leq 1, then endoscopic remission SES-CD \leq 4 is achieved.	Same as for endoscopic response
CDAI	Crohn's Disease Activity Index (CDAI) is an 8-item disease activity measure comprised of a composite of 3 patient-reported and 5 physician-reported/laboratory items (physical signs and a laboratory parameter [hematocrit]). Participant responses are summed over a 7-day period and all items are subsequently weighted, yielding a total score range of 0 to 600 points. All endpoints derived using participant responses will be calculated from daily diary data from the most recent 7 days (possibly nonconsecutive) out of the 12 days prior to the day of the visit, after removing the day(s) of the endoscopy prep,	Clinical remission by PRO	Clinical remission by PRO is defined as a stool frequency (SF) average ≤3 and abdominal pain (AP) average ≤1 with both values no worse than baseline. For each visit, AP average and SF average will be calculated from daily diary data by averaging the most recent 7 days in the 12 days prior to the day of the visit, after removing the day(s) of the endoscopy prep, the day of endoscopy procedure, and the 2 days following the endoscopy procedure. If SF average ≤ 3, AP average ≤ 1, SF average ≤ baseline SF average and AP average ≤ baseline AP average, then clinical remission by PRO is achieved.	Missing if less than 4 days of data are available at either baseline or endpoint
	the day of endoscopy procedure, and the 2 days following the endoscopy procedure. SF captures the number of liquid or very soft stools. AP score is classified as 0=none, 1=mild, 2=moderate, 3=severe.	Clinical response by PRO	Clinical response by PRO is defined as at least a 30% decrease in either SF or AP, and no worse than baseline. If [100 * (SF average – baseline SF average) / baseline SF average] ≤ -30 or [100*(AP average – baseline AP average) / baseline AP average] ≤ -30, and SF average ≤ baseline SF average and AP average ≤ baseline AP average, then clinical response by PRO is achieved.	Missing if less than 4 days of data are available at either baseline or endpoint

Measure	Description	Variable	Derivation / Comment	Definition of missing
Measure	Description	Variable CDAI total score	CDAI total score is based on the CDAI questionnaire in Appendix 7 in Section 6.7. It also utilizes the standard weights table in that section. 1.Patient-reported items from diary - the most recent 7 days are included (possibly nonconsecutive) out of the 4 weeks prior to corresponding visit after removing the day(s) of the endoscopy prep, the day of endoscopy procedure, and the 2 days following the endoscopy procedure. See Appendix 9. 2. Physician-reported questionnaire – from up to 4 weeks prior to actual visit 3.Hematocrit - central (or secondarily local) lab Hematocrit value associated with the Visit; if neither available, use closest result from 4 weeks prior to visit up to 12 weeks after visit except for Week 12; For Week 12/V4, 4 weeks before or after this visit. 4. Weight –weight associated with the Visit;	Definition of missing CDAI total score will be missing if any of its components are missing. If none of the options in Section 4 of the CDAI questionnaire is checked, it will be assumed that no extra- intestinal manifestations were present.
			4. Weight –weight associated with the Visit; If not available, closest to the visit in 6 months before or after the visit except for Week 12; For Week 12 use 12 weeks before or after this visit	
		Change from baseline in CDAI total score	Change from baseline in CDAI score is defined as CDAI score – baseline CDAI score.	Missing if CDAI total score is missing at baseline or at time point.

Measure	Description	Variable	Derivation / Comment	Definition of missing
		Clinical response by	Clinical response by CDAI is defined as a	Missing if CDAI total
		CDAI	decrease from baseline in the CDAI total	score is missing at
			score ≥ 100 and/or a CDAI total score ≤ 150 .	baseline or at time
				point.
		Clinical remission	Clinical remission by CDAI is defined as	Missing if CDAI total
		by CDAI		score is missing at time
				point.
		AP average	Description of AP average is provided as	Missing if less than
			part of the definition for clinical remission	4 days of data are
			by PRO.	available at time point
		Change from	Change from baseline in AP average is	Missing if AP average
		baseline in AP	defined as AP average – baseline AP	is missing at baseline
		average	average.	or at time point
		SF average	Description of SF average is provided as	Missing if less than 4
			part of the definition for clinical remission	days of data are
			by PRO.	available at time point
		Change from	Change from baseline in SF average is	Missing if SF average
		baseline in SF	defined as SF average – baseline SF	is missing at baseline
		average	average.	or at time point
Corticosteroid-	See CDAI sections above.	Corticosteroid-free	Achieving clinical remission by CDAI and	Missing if clinical
free endpoints		clinical remission	being corticosteroid-free ≥12 weeks prior to	remission by CDAI
		by CDAI	time point of interest.	missing
	See SES-CD section above.	Corticosteroid-free	Achieving alternate endoscopic remission	Missing if endoscopic
		endoscopic	SES-CD ≤ 4 and being corticosteroid-free	remission SES-CD ≤4
		remission	≥12 weeks prior to time point of interest.	is missing

Measure	Description	Variable	Derivation / Comment	Definition of missing
C (
IBDQ	Inflammatory Bowel Disease Questionnaire (IBDQ): A 32-item patient-completed questionnaire that measures 4 aspects of patients' lives: symptoms directly related to the primary bowel disturbance, systemic symptoms, emotional function, and social function (Guyatt et al. 1989; Irvine et al. 1994; Irvine et al. 1996). Responses are graded on a 7-point Likert scale in which 7 denotes "not a problem at all" and 1 denotes "a very severe problem."	IBDQ score	IBDQ total score is calculated as the sum of all questions. Scores range from 32 to 224; a higher score indicates a better quality of life.	If more than 4 questions are missing or more than 2 questions for any subscore are missing, then IBDQ Score is missing. Otherwise, missing questions imputed as the mean of the other items in each subscore.
		Change from baseline in IBDQ score	Change from baseline in IBDQ is defined as IBDQ total score – baseline IBDQ total score.	Missing if IBDQ score is missing at time point or baseline
		Bowel symptoms subscore	Calculated as the sum of questions 1, 5, 9, 13, 17, 20, 22, 24, 26, 29.	If only one question is missing, impute as the mean of the other
		Systemic symptoms subscore	Calculated as the sum of questions 2, 6, 10, 14, 18.	items in the subscore. Missing if more than one item in the
		Emotional function subscore	Calculated as the sum of questions 3, 7, 11, 15, 19, 21, 23, 25, 27, 30, 31, 32.	subscore is missing
		Social function subscore	Calculated as the sum of questions 4, 8, 12, 16, 28.	

Measure	Description	Variable	Derivation / Comment	Definition of missing
			Change from baseline in any one of the IBDQ subscores is defined as IBDQ subscore – baseline IBDQ subscore.	Missing if IBDQ subscore is missing at time point or baseline
		IBDQ response	≥16 point improvement from baseline in IBDQ score as described by Irvine et al. (1996).	Missing if either baseline or observed value is missing.
		IBDQ remission	IBDQ score ≥170 as described by Irvine (2008).	Missing if the IBDQ score is missing

[figure not shown]

Measure	Description	Variable	Derivation / Comment	Definition of missing
Extraintestinal manifestations	EIMs will be collected in the eCRF and include a. arthritis, arthralgia; b. iritis,	EIMs Count	EIMs count will be derived by summing the number of EIMs.	If the question is not answered, it will be
(EIMs)	uveitis; c. erythema nodosum, pyoderma gangrenosum, aphthous, stomatitis.	EIMs Presence	EIMs Count ≥1	missing Missing if EIMs Count is missing
Fistulae	Draining cutaneous and draining rectal/vaginal fistulae will be collected in the eCRF	Number of draining fistulae	Draining fistulae count will be calculated by adding the number of draining cutaneous and rectal/vaginal fistulae.	If the question is not answered, then it will be missing

Measure	Description	Variable	Derivation / Comment	Definition of missing
		Fistulae Presence	Number of draining fistulae ≥1	Missing if number of draining fistulae is missing
		Percent change from baseline in draining fistulae	The percent change reduction will be calculated by subtracting the number of draining fistulae at endpoint from the number of draining fistulae at baseline. The result is divided by the number of draining fistulae at baseline and multiplied by 100.	Missing if number of draining fistulae is missing at baseline or time point.
		At least 50% reduction in draining fistulae	Percent change from baseline in draining fistulae ≥50	Missing if number of draining fistulae is missing at baseline or time point.
Medical resource utilization and health economics	Crohn's related emergency room (ER) Visits, Hospitalizations, Surgeries related to Crohn's disease will be collected in the eCRF.	Crohn's related ER visits count, Hospitalizations count, and Crohn's related surgeries count.	For each participant the number of Crohn's related ER visits, the number of hospitalizations, and the number of Crohn's related surgeries will be calculated during the study.	
		Medical resource utilization presence	Crohn's related ER visits count, Hospitalizations count, or Crohn's related surgeries count ≥1	

Measure	Description	Variable	Derivation / Comment	Definition of missing
Biomarkers	C-reactive protein (CRP) is a biomarker of inflammation.	CRP	Lab value.	Single lab value. Missing if missing.
	Fecal calprotectin is used as a biomarker of intestinal inflammation in clinical practice.	Fecal calprotectin	Lab value.	Single lab value. Missing if missing.
RHI	The RHI (Mosli et al. 2015) is a histopathological index consisting of 4 items and each score from 0-3 (i.e., chronic inflammatory infiltrate level [x1], lamina	RHI segmental scores	The segmental score is calculated as sum of all items with multiplication factors.	Missing if samples are not collected or image is deemed unreadable.
	propria neutrophils [x2], neutrophils in epithelium [x3], erosion or ulceration [x5]). The total score of each segment ranges from 0 to 33, with higher scores indicating	RHI colonic score	Sum of the RHI segmental scores of 4 colon segments. The range is from 0 to 132.	Missing if all of the 4 colon segments are missing.
	If more than 1 image is available for a segment, the CR will score index components based on the worst features across the images and biopsy sections.	RHI total score	Sum of all 5 RHI segmental scores. The range is from 0 to 165.	Missing if all segments are missing.
GHAS	5		GHAS segmental score is in a range of 0 to 16 and is calculated by adding up the scores for each histological variable.	Missing if samples are not collected or image is deemed unreadable.
la p p c o o s	lamina propria [from 0-2], 4. Infiltration of polymorphonuclear cells in the lamina propria [from 0-2], 5. Polymorphonuclear cells in epithelium [from 0-3], 6. Presence of erosion and/or ulcers [0, 1], 7. Presence of granuloma [0, 1], 8. Number of biopsy specimens affected [from 0-3]).	Modified GHAS segmental scores	Modified GHAS segmental score is defined as the sum of 5 selected items (i.e., items 1, 3, 4, 5, and 6).	Missing if samples are not collected or image is deemed unreadable.
		Modified GHAS colonic score	Sum of 4 colon segmental modified scores.	Missing if all colon segments are missing
	Total score for each segment is in a range of 0 to 16.	Modified GHAS total score	Sum of all segmental modified scores.	Missing if all segments are missing

Measure	Description	Variable	Derivation / Comment	Definition of missing
	If more than 1 image is available for a segment, the CR will score index components based on the worst features across the images and biopsy sections.	Active GHAS segmental scores	Active GHAS segmental score is defined as the sum of 4 selected items (i.e., items 1, 4, 5, and 6).	Missing if samples are not collected or image is deemed unreadable.
		Active GHAS colonic score	Sum of 4 colon segmental active scores.	Missing if all colon segments are missing
		Active GHAS total score	Sum of all segmental active scores.	Missing if all segments are missing
		Histological response for segments, colonic segment (4-segment colon), total intestine	Histological response is defined as: Absence of neutrophils in epithelium and necessarily absence of epithelial damage, erosions, and ulcerations. Neutrophil infiltration of lamina propria is allowed. OR Decrease from the baseline RHI or active GHAS score (reduction of 50% from baseline)	Missing if GHAS score and sum of RHI items 2, 3, and 4 are missing at baseline or time of interest.
		Histological remission for segments, colonic segment (4-segment colon), total intestine	Absence of mucosal neutrophils (in both epithelium and lamina propria) and absence of epithelial damage, erosions, and ulcers.	Missing if GHAS score and sum of RHI items 2, 3 and 4 are missing.
Composite		Clinical remission by CDAI and endoscopic response	Achieved both clinical remission by CDAI and endoscopic response.	Missing if clinical remission by CDAI or Endoscopic response is missing.

Abbreviations: AP = abdominal pain; CDAI = Crohn's Disease Activity Index; CD = Crohn's disease; eCRF = electronic case report form; CRP = C-reactive protein;

EIM = extraintestinal manifestation; CCI

IBD = inflammatory bowel disease; IBDQ = Inflammatory Bowel Disease Questionnaire; MCID = Minimal clinical important difference; CCI

PRO = patient-reported outcomes; SES-CD = Simple Endoscopic Score for Crohn's Disease; SF = stool frequency; VAS = Visual Analog Scale; CCI

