5.1.2 Definition of Baseline

Unless otherwise specified, all references to baseline for efficacy and health-outcome-related endpoints in this study refer to baseline values of the originating study (that is, the study in which the participant received their first dose for the mirikizumab Crohn's Disease development program). Unless otherwise specified, all references to baseline for safety analyses refer to baseline values of Study AMAX.

Change from baseline will be calculated as the visit value of interest minus the baseline value. If a baseline value or the value at the visit is missing for a particular variable, then the change from baseline is defined as missing.

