5.1.5 Missing Data Imputation

Intercurrent events (FDA 2017) are events which occur after the study intervention initiation and make it impossible to measure a variable or influence how it should be interpreted. Section 1.1 includes intercurrent events for the primary and secondary endpoints. The missing data methods described below may be used to address the intercurrent event strategies proposed for this study.

Non-Responder Imputation

A hybrid estimand strategy will be used to handle binary endpoints:

- Patients who discontinue study treatment due to reasons other than commercial availability and extraordinary circumstances including study treatment supply issues and the site termination, are categorized as treatment failures after discontinuation. As such, these patients are not considered missing from the perspective of the estimand of interest.
- The hypothetical strategy will be used to handle the ICE of study treatment discontinuation due to commercial availability and extraordinary circumstances including study treatment supply issues and the site termination. Participants with the ICE will be excluded from analysis for timepoints of interest after the ICE. The assumption behind this approach is that measurements after this ICE are missing completely at random and thus the estimation can be implemented using observed values.

^a Unless otherwise specified, these treatment arms are not included in the modeling to estimate treatment effect for MMRM and ANCOVA analysis. Also these treatment arms may be excluded from some tables or figures to simplify the output.

A small number of patients who completed study treatment up to the time point of interest but are sporadically missing the binary endpoint data will still require imputation. These patients will be imputed using NRI.

Modified Baseline Observation Carried Forward (mBOCF)

As a primary analysis for continuous variables, the ANCOVA with mBOCF approach will be used for handling missing data. For continuous endpoints a hybrid estimand strategy is used:

- For ICEs of study intervention discontinuation due to reasons other than commercial
 availability and extraordinary circumstances including study treatment supply issues and
 the site termination, the composite strategy will be used such that measurements after the
 ICEs will return to baseline. As such, these patients are not considered missing from the
 perspective of the estimand of interest.

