For the co-primary endpoints and selected secondary endpoints, missing data will be imputed using hybrid multiple imputation as a sensitivity analysis. Missing data for reasons of treatment discontinuation due to commercial availability and extraordinary circumstances including study treatment supply issues and the site termination will be imputed by multiple imputation (MI), while missing data due to treatment discontinuation for reasons other than commercial availability and extraordinary circumstances including study treatment supply issues and the site termination will be categorized as non-responders. Sporadically missing data (i.e., when a patient was still in the treatment period but data was not collected) will be imputed by MI.

As Observed Analysis

For some endpoints, patients who are missing the endpoint data for a specific visit for any reason including intercurrent events will be excluded from the analysis for that visit. Simple descriptive summaries will be presented.

[figure not shown]

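### SAP Appendix 1 treats clinical response by CDAI as missing when baseline CDAI is missing, even if a visit score of 150 or less already meets the definition

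*SAP*

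**What the plan says.** The CDAI rows of SAP Appendix 1 (Section 6.1) give a definition and a missing rule for each variable.

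- **Clinical response by CDAI.** A decrease from baseline in total "score ≥ 100 and/or a CDAI total score ≤ 150". Its missing rule covers a total score absent at "baseline or at time" point.
- **Change from baseline in CDAI total score.** "Missing if CDAI total score is missing at baseline or at time point". This is the same rule, on a variable that cannot be computed without a baseline.
- **Clinical remission by CDAI.** Missing only where the total "score is missing at time" point. Baseline plays no part.
- **CDAI total score.** "CDAI total score will be missing if any of its components are missing".

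SAP Section 5.1.2 fixes the baseline: "all references to baseline for efficacy and health-outcome-related endpoints in this study refer to baseline values of the originating study".

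SAP Appendix 2 (Section 6.2) lists clinical response by CDAI for NRI, mNRI and as-observed analysis in the primary analysis set. Section 5.1.5 says how each treats a missing binary endpoint.

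- **NRI.** Participants who stayed on treatment to the time point but "are sporadically missing the binary endpoint data will still require imputation. These patients will be imputed using NRI".
- **mNRI.** "Sporadically missing data (i.e., when a patient was still in the treatment period but data was not collected) will be imputed by MI".
- **As observed.** A participant without the endpoint at a visit is left out of that visit.

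**The concern.** The two conditions for response are alternatives, and the second uses the visit score alone. The missing rule nevertheless demands a baseline for both, so it discards a status that is already determined. The rule suits change from baseline. It does not suit an endpoint that can be met without a baseline.

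Two things follow. The response proportion, a secondary endpoint at Week 52 and other visits, loses people who meet its written definition. And because the remission row ignores baseline, one participant at one visit can appear as a CDAI remitter and a CDAI nonresponder, which a reader of the tables would find hard to explain.

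The protocol does not ask for this. Its NRI trigger in Section 9.4.1.4 is missing data at the time point of interest, and here the visit score is present. SAP Section 6.3 declares no change to protocol-planned analyses, so the baseline requirement is not presented as a deliberate departure.

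**Working it through.** The documents state no figure that depends on this rule, so there is none to reproduce. The check has two parts.

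**1. Apply the row as written.** Take baseline CDAI as missing, 320, 220 or 180, and visit CDAI as 120, 150, 200 or 260, for a participant still on treatment. Compare the written definition with the SAP row followed by NRI.

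| Baseline | Visit | Definition | SAP row | After NRI |
|---|---|---|---|---|
| missing | 120, 150 | response | missing | nonresponse |
| missing | 200, 260 | undetermined | missing | nonresponse |
| 320 | 120, 150, 200 | response | response | response |
| 320 | 260 | nonresponse | nonresponse | nonresponse |
| 220, 180 | 120, 150 | response | response | response |
| 220, 180 | 200, 260 | nonresponse | nonresponse | nonresponse |

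The 12 cells with a baseline agree throughout. The only wrong classification is in the first row: no baseline and a visit score of 150 or less. In the second row the status is truly unknown, and imputation is appropriate.

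For the first-row participant, mNRI draws a status by multiple imputation and the as-observed analysis drops the person. None of the three planned analyses uses the known status.

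One reading is needed here. A missing baseline removes the endpoint at every visit, which is not sporadic in the ordinary sense. Section 5.1.5 offers no other category for a participant still on treatment, so the sporadic rules are taken to apply.

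**2. Size under NRI.** Let m be the share of participants with no baseline CDAI and q the share of those with a visit score of 150 or less. Each such participant moves from nonresponse to response when the rule is corrected, so

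understatement = m × q.

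The documents give neither quantity. With q assumed between 0.4 and 0.7:

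| m (assumed) | m × 0.4 | m × 0.7 |
|---|---|---|
| 0 | 0 | 0 |
| 0.5% | 0.20 points | 0.35 points |
| 1% | 0.40 points | 0.70 points |
| 2% | 0.80 points | 1.40 points |
| 5% | 2.00 points | 3.50 points |

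For scale, assume a group of 200, 70% response among those with a baseline, m = 2% and q = 0.7. As written, 0.70 × 196 = 137.2 responders, or 68.6% (Wilson 95% interval 61.9 to 74.6). Corrected, 137.2 + 0.7 × 4 = 140.0, or 70.0% (63.3 to 75.9). The shift is small beside the width of either interval.

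**The case against.** The strongest reply is that nobody may be affected. The baseline belongs to the originating study, whose derivation rules and completeness are not in these documents. The criterion that defines the primary analysis set is redacted, so one cannot tell whether any member lacks a baseline CDAI. That stands: the size is unknown and zero is possible.

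A reader might infer that baseline CDAI is easily missing, because any one of eight missing components removes the total. The documents do not support this. The CDAI total score row has fallback windows for diary items, physician items, hematocrit and weight, and treats an unchecked extra-intestinal section as none present. How baseline was handled in the originating studies cannot be seen.

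A reader might also take an effect of 1 to 3 points from plausible-looking inputs (0.02 × 0.50 to 0.05 × 0.60). Those inputs are assumptions. The legible secondary objective for CDAI response concerns AMAM participants who had not achieved endpoints at Week 52 of that study, where a share of 50% to 60% at or below 150 may be too high.

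A further reply is that dropping the baseline requirement everywhere would do harm, and this also stands. In the as-observed analysis, participants without a baseline would enter only when they respond. Assume 1,000 participants, 950 with a baseline and 70% of those responding (665), and 50 without, of whom 60% (30) score 150 or less. Keeping the baseline requirement gives 665/950 = 70.0%. Dropping it gives 695/980 = 70.9%, with the other 20 excluded because of their outcome.

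Finally, the study tests no hypotheses and makes no treatment comparisons, and the NRI error runs in the conservative direction. Both are true and limit the importance. Neither makes the classification right.

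**Conclusion.** The point holds as a drafting error of minor weight. The missing rule for clinical response by CDAI contradicts the definition beside it, and no other text in the protocol or SAP overrides it. Under NRI a participant who meets the definition is counted as a nonresponder; under mNRI a known status is imputed.

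Only participants with no originating-study baseline CDAI and a visit score of 150 or less are misclassified. The understatement is m × q, probably under a point or so unless several percent lack a baseline, and zero if none do.

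A reader might infer that the co-primary CDAI remission result is also at risk. It is not: its missing rule uses the visit score alone. The remission cutoff is redacted, so the possibility of remission without response rests on the two differing missing rules. It is a contradiction of the written definitions wherever the visit score is 150 or less.

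**What to change.** In SAP Appendix 1, replace the missing rule for clinical response by CDAI, for the NRI and mNRI analyses, with:

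*Response is achieved if the CDAI total score at the time point is 150 or less, whether or not baseline is available; otherwise missing if the CDAI total score is missing at baseline or at the time point.*

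For the as-observed analysis, keep the requirement for a baseline value and say so. The rules in Section 5.1.5 for treatment discontinuation continue to take precedence in the imputed analyses.

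The result for every participant with a baseline is unchanged under NRI, and no new data are needed. The cost is that the missing rule then differs between the imputed and as-observed analyses, which takes one extra line in the SAP and in the derivation program. Reporting the number of participants with no baseline CDAI would show whether the point had any effect.
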